In addition to the medical history and medication questionnaires, participants will also be given a risk stratification questionnaire at the first screening visit. The purpose of this questionnaire is to determine if participants will need medical clearance prior to enrolling into an exercise program. The determination is based on the presence/absence of cardiovascular/pulmonary/metabolic disease risk factors, sign and symptoms, and known medical history. The following schematic demonstrates how medical clearance will be determined (Figure 1). The American College of Sports Medicine recommends that all patients are first screened to determine if they are participate in regular exercise (defined as performing planned, structured physical activity at least 30 min at moderate intensity on at least 3 days per week for at least the last 3 months). If the participant responds with no medical clearance will be not be needed for those who have not been diagnosed with any CV, Metabolic, or renal disease and are showing no signs/symptoms. If the response is yes those who have not been diagnosed as well as those with a diagnosis and are asymptomatic will not need physician clearance [6]. Like the previous recommendations this is only for moderate intensity exercise. Our exercise protocol falls within this moderate intensity range. The original protocol called for participants to exercise in the range of 50-75% of their maximal heart rate reserve (i.e., moderate to high intensity). The range was previously modified

to 40-60% of maximal heart rate reserve (i.e., moderate intensity). Hence, participants that have no diagnosis of CV, Metabolic, or renal disease or those that have been diagnosed but are asymptomatic will be enrolled without the need for physician clearance. *Those who have signs and symptoms or who have been diagnosed but do not meet the exercise criteria will require medical clearance from their physician.* Final approval and acceptance into the program for patients will be provided by our study physician. It's worth noting the risk of serious adverse events occurring during properly supervised exercise is extremely low (< 1 per 100,000 hours of exercise) even in older adults, with cardiovascular disease. Blood pressure will also be measured.

Figure 1: Exercise preparticipation health screening logic model for aerobic exercise participation [6]

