Physical Activity. The Physical Activity Scale for the Elderly (PASE) has proven reliable in many of our clinical trials, including a group of 254 men and women aged ≥ 65 yrs [22].

Cognitive Functioning/Depression. The Mini Mental State Exam (MMSE) will be used to measure cognitive function and has been measured in older American Indians [23]. Depression will be measured using the Center for Epidemiologic Studies Depression Scale [24]. This measure has previously been validated with older American Indians in the Great Lakes region [25].

Inclusion/Exclusion Criteria

Inclusion Criteria:

- (1) Age ≥ 50 years
- (2) Knee Pain plus ACR Criteria for Knee Osteoarthritis
- (3) $\text{BMI} = 25 \geq \text{kg/m}^2$

Exclusion Criteria:

Submission Date: 9.9.22

1. Significant co-morbid disease that would threaten safety or impair ability to participate in interventions or testing (Method: Medical history; medications; physical exam; telephone pre-screen; risk stratification)
 - a. Blindness
 - b. Type 1 diabetes
 - c. History or symptoms of coronary artery disease or pulmonary disease with no medical clearance (symptoms include angina, unreasonable breathlessness, dizziness/fainting/blackouts)
 - d. Unable to walk without a device
 - e. Lower extremity fracture (within previous 3 months)
 - f. Joint Replacement (excluded if double KR or within previous 6 months)
 - g. Knee injection or surgery (within previous month)
 - h. Lower extremity injury that affects activities of daily living
2. Not sufficiently overweight or obese, $BMI < 25 \text{ kg/m}^2$ (Method: Ht/Wt)
3. Not having knee pain: (Method: < 1 on the pain scale, WOMAC and Telephone Screen)
4. Inability to finish pilot study or unlikely to be compliant (Method: Telephone Screen, Screening Interviews)
 - a. Planning to leave area > 1 month during the next 3 months
 - b. Unwilling to change eating or physical activity habits
 - c. Unwilling to attend exercise/diet sessions
 - d. Participating in another intervention study (only if the other study has requested they not be enrolled)
 - e. Living > 30 minutes from the intervention site
5. Age, age < 50 (Method: Telephone Screen & Demographics Forms)
6. Other conditions that may prohibit the effective delivery of the intervention (Method: Telephone Screen)
 - a. Unable to provide own transportation to exercise center
 - b. Unable to read or write, cannot speak or read English

Community Advisory Board

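### The medical-clearance rule contradicts itself in adjacent sentences: one waives physician clearance for people for whom the next requires it

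*Protocol*

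**What the plan says.** The paragraph on the risk stratification questionnaire (Protocol, Measures, under Medical History, Medications, and Blood Pressure) first reports a published recommendation that depends on whether a person already exercises regularly.

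- Non-exercisers skip clearance only if they are people "who have not been diagnosed with any CV, Metabolic, or renal disease and are showing no signs/symptoms".
- For regular exercisers the exemption is wider: the undiagnosed, and also "those with a diagnosis and are asymptomatic will not need physician clearance".

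After explaining that the trial's exercise is of moderate intensity, the Protocol draws its own conclusion in a sentence beginning *Hence*. That sentence covers two groups. The first is "participants that have no diagnosis of CV, Metabolic, or renal disease". For the second, "those that have been diagnosed but are asymptomatic will be enrolled without the need for physician clearance".

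The next sentence, set in italics, reads "Those who have signs and symptoms or who have been diagnosed but do not meet the exercise criteria will require medical clearance". The paragraph then gives the study physician the final say on entry.

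Under Exclusion Criteria, item 1c separately excludes "History or symptoms of coronary artery disease or pulmonary disease with no medical clearance".

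**The concern.** The *Hence* sentence is the point at which the Protocol turns a general recommendation into a rule for this trial. It drops both conditions on which the recommendation depends: exercise status for people with a diagnosis, and symptoms for people without one. The sentence after it restores both conditions as requirements. Nothing in the wording (no *except*, no *unless*) makes the second sentence a limit on the first.

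Staff who apply the *Hence* sentence would not ask for a clearance that the next sentence demands. The people concerned are those for whom screening matters: sedentary participants with a known cardiovascular, metabolic or renal diagnosis, and participants who report signs or symptoms but have no diagnosis. Two screeners could handle the same person differently, and each could cite the Protocol.

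**Working it through.** No statistical quantity enters this point, so the check is a comparison of the rules. Each person is classified by diagnosis (cardiovascular, metabolic or renal), by signs or symptoms, and by whether they meet the regular-exercise criteria. This gives 2 × 2 × 2 = 8 combinations. The third rule column shows the recommendation for the person's exercise status, as the paragraph reports it.

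| Diagnosis | Symptoms | Regular exerciser | Reported recommendation | *Hence* sentence | Next sentence | Do the last two agree? |
|---|---|---|---|---|---|---|
| no | no | no | waived | waived | not required | yes |
| no | no | yes | waived | waived | not required | yes |
| no | yes | no | not waived | waived | required | **no** |
| no | yes | yes | unclear | waived | required | **no** |
| yes | no | no | not waived | waived | required | **no** |
| yes | no | yes | waived | waived | not required | yes |
| yes | yes | no | not waived | not waived | required | yes |
| yes | yes | yes | not waived | not waived | required | yes |

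The entry marked unclear arises because the symptom condition in the sentence on regular exercisers can be read as covering both groups or only the diagnosed.

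1. The two sentences conflict in 3 of the 8 combinations: diagnosed, asymptomatic non-exercisers, and undiagnosed people with symptoms at either level of exercise.
2. In the two conflicting rows where the reported recommendation is clear, it agrees with the next sentence and not with *Hence*. The intended rule is therefore very likely that clearance is required.
3. If *Hence* waived clearance only for undiagnosed people without symptoms (rows 1 and 2) and for diagnosed, asymptomatic regular exercisers (row 6), the next sentence would require it in exactly the other five rows. All 8 rows would then agree.

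Item 1c only partly covers the gap. Read literally, it blocks uncleared people with a history or symptoms of coronary disease. It does not name other cardiovascular, renal or metabolic diagnoses, apart from type 1 diabetes, which item 1b excludes outright. Read as applying only where clearance is required, it refers back to the risk stratification paragraph and inherits the contradiction.

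**The case against.** The strongest reply is that a careful reader can recover the intended rule. The italic sentence comes last, is more specific, is emphasised, and matches the earlier rule for non-exercisers. On that view one loose summary sentence stands against two consistent ones. This is a good argument about intent, and it explains why the impact is small. It does not remove the contradiction, because a screening rule should not depend on the reader working out which of two adjacent sentences prevails.

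Second, the paragraph points to Figure 1 for the determination, and the figure is not reproduced in the text available here. It may well show the correct logic. It could not make two opposite sentences agree, but its absence means that nobody can say staff would in fact omit a clearance.

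Third, the study physician approves every entry. That is a genuine backstop. The paragraph treats it, however, as separate from clearance by the participant's own physician, so it does not settle whether that clearance must be sought.

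Fourth, the Protocol's own figure for supervised exercise is below 1 serious event per 100,000 hours. Even if all 30 participants attended three one-hour sessions a week for 13 weeks, that is 3 × 13 = 39 hours each and 30 × 39 = 1,170 hours in total, or fewer than 1,170 / 100,000 ≈ 0.012 expected events. This supports calling the impact minor. The limitation is that the Protocol does not say whether the exercisers behind that rate had been medically cleared.

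A reader might also infer a second contradiction: item 1c excludes uncleared people with a coronary history, while an asymptomatic regular exerciser with such a history is told that no clearance is needed. The documents do not firmly support this. Item 1 gives its methods as "Medical history; medications; physical exam; telephone pre-screen; risk stratification", so 1c can fairly be read as clearance that the risk stratification calls for and that was not obtained. Even taken literally, 1c is only the stricter of the two texts.

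**Conclusion.** The contradiction is real and lies within one paragraph. The *Hence* sentence waives clearance in three of eight participant profiles for which the following sentence requires it. It is a drafting error in a safety-screening rule; no design decision is in question.

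Its impact is minor. It affects whether some clearance requests are made, it is backed by the study physician's approval and in part by item 1c, and it has no bearing on sample size or analysis. The number of people affected cannot be derived, because the Protocol gives no prevalence of diagnoses, symptoms or regular exercise among those screened.

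A reader might infer that at-risk participants will exercise uncleared and come to harm. The documents do not support that: the figure is not visible, the backstops exist, and the stated event rate is very low. The conclusion rests only on the wording of the two sentences. The view that the italic sentence is the intended rule is an inference from its agreement with the rule for non-exercisers.

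**What to change.** Reword the *Hence* sentence so that clearance is waived only for (i) participants with no cardiovascular, metabolic or renal diagnosis and no signs or symptoms, and (ii) participants with such a diagnosis who are asymptomatic and meet the regular-exercise criteria. The italic sentence can stay as it is. Check that Figure 1 and the screening form show the same rule.

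Optionally, in the same amendment, state that item 1c refers to clearance required by the risk stratification and not obtained. This should not be done alone: while the *Hence* sentence stands, tying 1c to it could loosen the safeguard for non-exercisers with a coronary history.

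The cost is one amended sentence, a matching form, and a few clearance requests, in a number that the document does not allow to be derived.

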Participants (age \geq 50 years; BMI \geq 25 kg/m²) will be randomized to one of 2 groups: diet-induced weight loss and exercise or an attention control group. The sample will consist of 30 ambulatory, community-dwelling persons that meet the ACR clinical criteria for knee osteoarthritis.

Primary Hypothesis and Aim

Hypothesis 1. The study will demonstrate the feasibility of conducting a trial similar to WE-CAN in Cherokee, NC that will recruit American Indian participants. It will leverage the organizational structure and expertise of the parent WE-CAN pragmatic, community-based trial.

Aim 1. To conduct a trial in Cherokee, NC that will be comprised of (a) 90% participants who self-identify as American Indian,, including but not limited to the Eastern Band Cherokee Indian Tribe, and who are older, overweight or obese with symptomatic knee OA; (b) the executive clinical director of Cherokee Indian Hospital to act as site PI and co-investigator of the parent

trial; (c) local community based American Indian staff trained by our coordinating center to deliver the intervention; and (d) an American Indian Community Advisory Board.

Secondary Hypothesis and Aim

Hypothesis 2. A subgroup analysis of the American Indian participants will provide pilot data of whether a pragmatic, diet-induced weight-loss and exercise intervention implemented by local American Indian personnel will reduce knee pain and improve self-reported function, mobility, and health-related quality of life compared to an attention control group.

Aim 2. To determine whether a pragmatic, community-based 3-month, diet-induced weight-loss and exercise intervention reduces knee pain, measured by the Western Ontario McMasters Universities Osteoarthritis Index (WOMAC), and improves WOMAC self-reported function, health-related quality of life as measured by the physical subscale of the SF-36 questionnaire, and 6-minute walk distance (an accepted measure of mobility) in overweight and obese American Indian older adults with knee OA compared to an attention control group.

Study Design

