We will randomize 30 overweight and obese ($BMI \geq 25 \text{ kg/m}^2$), adults age ≥ 50 yrs knee OA into one of 2 groups: an intensive dietary restriction-plus-exercise (D+E) group or an attention control (nutrition and health) group. Our minimum weight-loss goal for the weight-loss group will be 5% of body weight. The exercise intervention will meet 3 days/wk at the clinical site. The intervention will be comprised of both aerobic and strength training exercises. The nutrition and health group will meet 2 times over a 3 month period and will also receive a combination of text messages, emails (via personal email or Facebook), phone calls, and mailings for the remaining months. Participants will be allowed to choose their preferred method.

Measures

Western Ontario McMasters Universities Osteoarthritis Index (WOMAC). We will measure self-reported physical function and pain using the WOMAC (scores will be pulled from the KOOS Questionnaire in which the WOMAC is embedded). The LK version asks participants to indicate on a scale from 0 (none) to 4 (extreme) the degree of difficulty experienced in the last week due to knee OA. Individual scores for the 17 items are totaled to generate a summary score that could range from 0-68, with higher scores indicating poorer function. The pain index assesses participants' pain on the same scale, ranging from 0 (none) to 4 (extreme). The pain subscale consists of 5 items and total scores can range from 0-20, with larger scores indicating greater dysfunction. This instrument has been validated and recommended by the Osteoarthritis Research Society as the health status measure of choice in older adults with knee OA. In order to measure the minimal clinically improvement difference (MCID) participants will be asked to compare their knee pain to how it was at the beginning of the study.

Mobility. Our primary mobility measure will be 6-minute walk distance. Participants are told to walk as far as possible in 6 minutes on an established course. No personal timing devices are permitted, and participants are not provided feedback during the test. Results are significantly correlated to treadmill time and symptom-limited maximal oxygen consumption ($r = 0.52$ and $r = 0.53$, respectively) and have a 3-month test-retest reliability of 0.86 (Pennix et al). The Short Physical Performance Battery (SPPB) will also be used to measure mobility (Guralnik et al).

Submission Date: 9.9.22

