We created an American Indian Community Advisory Board as a part of the revision that was submitted to NIH. The investigators plan to involve the community advisory board with the pilot study. The board includes [name], Chair of the North Carolina American Indian Health Board, [name], a pathologist and native Eastern Band Cherokee Indian and former board member of Cherokee Indian Health, and [name], program director of Cherokee Choices. We also will be working with [name], professor at Western Carolina University, as a consultant for the study.

Interventions

Diet-induced weight loss plus exercise

Month 1

There will be two individual sessions per month and 2 group sessions per month. The behavioral sessions will focus on awareness of changing eating habits to lower caloric intake. Educational content information regarding what food changes to make, how to make them, and why they are important will be clearly explained and discussed with participants and significant others. Each group session will include problem solving, review of a specific food topic, and tasting of several well-balanced, low-fat, nutritious foods prepared with widely available ingredients. During the individual sessions, the counselor will review individual progress, solve problems, answer questions, and set goals. During the initial individual session, the nutrition counselor will give the participant a weight history background questionnaire. The major emphasis for Period 1 is to enhance participant awareness of the importance and the need to change eating habits, i.e. lower caloric intake for weight loss. Each participant should be given the opportunity to practice skills using goal setting in a stepwise approach. Participants will follow a weekly menu plan which will incorporate meal replacements into their diet plan. Lean Shakes, a General Nutrition Center (GNC), product will be the meal replacement used. Participants may replace the Lean Shakes with a healthy, low-calorie meal of their choice, such as Lean Cuisine. Motivation and encouragement through the combined efforts of the nutrition counselor, the participant, significant others and the nutrition staff will enhance adherence.

Month 2

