In period 2 participants will focus on continued weight loss to reach the study weight loss goal of 5% of baseline weight. Participants will follow a weekly menu plan with recipes using traditional foods and the option to incorporate meal replacements. The traditional meals will contain 400-600 kcals, be low in fat and added sugars, and high in vegetables, fruits, and whole grains. Snacks may be a bar, fruit, or vegetable providing ~100-120 kcals. Daily caloric intake for each participant will be adjusted to his or her rate of weight change. Each group will be encouraged to take a daily multivitamin/mineral supplement containing no more than 100% of the Dietary Reference Intake for any particular nutrient.

Month 3

Period 3 will emphasize weight management over time. Participants will continue to follow a weekly menu plan with recipes using traditional foods and the option to incorporate meal replacements.

The exercise intervention will cover a 3-month period. The exercise program will consist of a 15-minute aerobic phase, a 20-minute strength-training phase, a second 15-minute aerobic phase, and a 10-minute cool-down phase. These sixty-minute exercise sessions will be conducted three days per week. Each participant will be prescribed an individual walking prescription by the exercise leader, which will be adjusted accordingly, as each

participant progresses throughout the 3 months. The exercise will be of moderate intensity. Alternate forms of aerobic exercise, such as but not limited to stationary bike, elliptical trainer, or treadmill walking, can be used in place of over-ground walking. This choice could be based on participant preference, the limitations of the exercise facility, or the participant's pain level.

Intervention Locations: The diet and exercise classes will be held at the Ginger Welch Complex.

All intervention staff in the WE-CAN study will be CPR certified. The exercise coordinator, who is part of the coordinating center and is responsible for maintaining exercise protocol congruity, will train and supervise the intervention staff. Intervention staff will meet monthly with the exercise coordinator to discuss any potential problems, risks, and concerns that have risen. AEDs will be available at each location. Emergency drills will be performed monthly in addition the AED will be checked monthly.

Nutrition & Health Intervention

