The nutrition and health (attention control) intervention will cover a 3-month period. There will be two total face to face group meetings over the 3 months, with one meeting each at months 1 and 3; and during the other month (month 2) participants will receive a combination of text messages, emails, and phone calls. Participants will be able to select their preferred method. Each group meeting will last approximately one hour and will be held at the Ginger Welch Complex in Cherokee, NC. The sessions will be interactive and will provide useful information on nutrition and general health topics. The Community Advisory Board will give input on the class sessions.

Procedures-Screening and Follow-up Visits.

Measurements	PSV	SV1	RV	FU3	Explanation
Informed Consent		x			
Questionnaires					
Eligibility Questionnaire	x				To determine eligibility
Medical History/Med History FU	xc	x		x	For eligibility and to document changes in health
Risk Stratification	xc	x			Used to screen cardiovascular risk
Comorbidities Questionnaire		x		x	
Randomization		x			
WOMAC		x		x	Pain is primary and function secondary outcomes. Will be taken from the KOOS
Knee Injury and Osteoarthritis Outcome Score (KOOS)		x		x	Assesses patient's opinion about their knee and associated problems
PASE scale		x		x	Physical Activity Scale for the Elderly
MOCA		x		x	Montreal Cognitive Assessment
EuroQol Quality of Life(EQ5D)		x		x	Quality of life measure
Resource Utilization		x		x	Visits to clinicians, tests, medications, injections, surgery, alternative therapies
Work Productivity and Activity Impairment Index		x		x	assesses absenteeism and presenteeism
DHQ II		x		x	NIH Diet History Questionnaire
SF-36		x		x	Health related quality of life (physical, mental)
Health Literacy		x		x	
Adherence Self Efficacy		x		x	Confidence in exercising at various intensities and frequencies
Adherence for Duration		x		x	Confidence in walking for different durations
Gait Efficacy		x		x	Confidence in completing tasks
Demographics		x			
Medication form		x		x	Atherosclerosis Risk in Communities form
Weight Efficacy Questionnaire		x		x	Self-Efficacy for Weight Management
PANAS		x		x	Positive and Negative Affect Scale
SWL		x		x	Satisfaction with Life
Perceived Stress		x		x	Stress
Pain Catastrophizing Scale		x		x	Catastrophizing
Intermittent and Constant Osteoarthritis Pain (ICOAP)		x		x	Intermittent and Constant Pain
CES-D		x		x	Depression
Transition Questionnaire				x	Knee pain

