The Data Management Group, part of the Coordinating Center, has primary responsibility for randomization and analyzing data generated by the clinical centers. Data will be collected on hard-copy forms at each site and transformed to an electronic database. Our web-based management system will assure integrity and validity. Dynamic reports and periodic statistical analyses will monitor quality. A participant-based inventory system will track recruitment, retention, adherence, and missing data from entry through exit, close-out, and lock-down of final datasets. Our team developed a similar database for the IDEA and START studies.

Statistical Analyses

Statistical analyses will be conducted according to intention-to-treat principles using SAS.

References:

2. Losina E, Burbine, Weinstein, AM, Reichmann WM, Rome BN, Collins JE, et al. Projecting the Future Public Health Impact of the Trend Toward Earlier Onset of Knee Osteoarthritis in the Past 20 Years. 2014;

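### Do the loosely described control contacts and diet-session counts, or the attention-control label, undermine the comparison?

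*Protocol*

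**What the plan says.** **Control arm.** Study Design states: "The nutrition and health group will meet 2 times over a 3 month period". It then lists remote contact by "text messages, emails (via personal email or Facebook), phone calls, and mailings for the remaining months". Nutrition & Health Intervention gives the same number of meetings and places them: "There will be two total face to face group meetings over the 3 months, with one meeting each at months 1 and 3". On remote contact it says that "during the other month (month 2) participants will receive a combination of text messages, emails, and phone calls". Both sections let participants choose the mode. Neither gives a number of remote contacts.

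**Weight-loss and exercise arm.** Under Month 1 the protocol says: "There will be two individual sessions per month and 2 group sessions per month". The Month 2 and Month 3 text covers diet content and menu plans but gives no session count. On exercise: "These sixty-minute exercise sessions will be conducted three days per week". Study Design gives the same weekly frequency, and the programme lasts 3 months.

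**Use of these items.** Aim 2 looks for benefit "in overweight and obese American Indian older adults with knee OA compared to an attention control group". Data Management says: "A participant-based inventory system will track recruitment, retention, adherence, and missing data from entry through exit". Statistical Analyses specifies intention to treat.

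**The concern.** Three things look wrong.

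- The two descriptions of the control's remote contact differ in mode (mailings or none) and in timing (several months or month 2 only). Staff working from one section might deliver something other than staff working from the other, and with no planned number, delivery cannot be checked against a target.
- The diet-session frequency appears under one month's heading. If it covers that month alone, 4 sessions are planned; if it recurs, 12. Someone who attends 4 would be fully adherent on one reading and one-third adherent on the other. In a feasibility pilot that tracks adherence, this looks awkward.
- Calling the comparator an attention control suggests that contact is roughly balanced. It is not, and the main Aim 2 outcomes, pain and function on the WOMAC, are self-reported and could respond to contact itself.

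At stake would be an uninterpretable adherence figure, an undefined comparator, and a treatment effect credited to diet and exercise when part of it came from staff attention.

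**Working it through.** The protocol states no total of contacts, so there is no figure to reproduce. The counts below come from its schedule, taking 3 months as 12 to 13 weeks (an assumption).

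**1. Control months and modes**
- Months without a meeting: 3 − 2 = 1. The plural in Study Design therefore does not fit, but only once the meeting months given in the intervention section are applied; Study Design does not say when the meetings fall.
- The sections agree on two meetings, on text, email and telephone, and on participant choice of mode. They differ on mailings and on the months.

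**2. Weight-loss arm sessions**
- Exercise: 3 × 12 = 36 to 3 × 13 = 39.
- Diet: (2 + 2) × 1 = 4, or (2 + 2) × 3 = 12.
- Total: 36 + 4 = 40 to 39 + 12 = 51. Counting all of these as in-person assumes the individual diet sessions are face to face, which the protocol does not state.
- Share that is exercise, and so not in doubt: lowest 36/48 = 75%; highest 39/43 = 91%.

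**3. Effect of the diet reading on adherence**
- Four sessions attended: 4/4 = 100% or 4/12 = 33%.
- The frequency is expressed twice as a rate per month, which would be redundant if it covered one month only. The diet programme continues through Months 2 and 3 with weekly menu plans, and nothing says that sessions stop. The wording points to recurrence without saying so outright.
- At reporting, the sessions actually offered will be known, so attendance can be given as a count and as a share of sessions offered, whichever reading was followed.

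**4. Contact ratio**
- Sessions: 40/2 = 20 to 51/2 = 25.5, leaving out remote contact.
- Exercise alone, in hours: 36/2 = 18 to 39/2 = 19.5, with control meetings of about one hour.
- Remote contacts have no stated number. If 8 are assumed, the ratio of all contacts is 40/10 = 4.0 to 51/10 = 5.1; if 30, it is 40/32 = 1.25 to 51/32 = 1.6. These are illustrations only, and a text message is not equivalent to an hour's session.
- The imbalance in face-to-face contact is large on any reading. With 12 weeks of exercise, the diet ambiguity moves the ratio only from 40/2 = 20 to 48/2 = 24.

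**5. What depends on these counts**
- Aim 1 concerns the make-up of the sample, site leadership, local staff and the advisory board. It sets no attendance threshold.
- Aim 2 compares randomised groups by intention to treat, so attendance does not decide who is analysed or in which arm.
- No sample-size or error-rate figure uses a contact count.

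**The case for a change.** The strongest case for a change is that intervention content belongs in the protocol and cannot be left to an analysis plan. Local staff are to deliver the programme from this text. Because participants choose their mode of contact, one who prefers post can be served under Study Design but not under the intervention section. A feasibility pilot should also be able to say what was planned as well as what was delivered, and a few sentences would settle it.

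Much of this is true as description. The two sections do differ, and the number of remote contacts is unstated. But staff are trained by one coordinating center and both arms' group sessions are at one venue, so divergent delivery is unlikely. Variation in mode is built into the design. Adherence denominators are commonly set in the analysis plan, which is not shown here.

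On the label, what stands is that unequal contact may contribute to a difference in self-reported pain. However, the protocol never claims that contact is matched. Comparing a whole programme with a low-contact control is a reasonable choice for a pragmatic pilot, and matching 36 to 39 hours of exercise contact would make it a different trial.

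**Conclusion.** No change to the plan is needed. The control-arm mismatch (mailings, and one month or more) is a clerical slip between a summary and a detailed section, to be reconciled whenever the text is next edited. The diet-session count is an ambiguity of placement that analysts can handle by reporting attendance against sessions offered. The label is a matter of wording.

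The size is modest: 8 diet sessions (12 − 4) are in doubt, while the 36 to 39 exercise sessions and the two control meetings are settled. The imbalance of at least 20 to 1 in sessions, remote contact aside, is real, but it follows from the chosen comparison. Reporting should describe the Aim 2 contrast as the effect of the whole package, contact included.

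This conclusion assumes that 3 months means 12 to 13 weeks, that delivered sessions are recorded as Data Management implies, and that no adherence criterion for success is set elsewhere.
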